4.2.2.2. Inclusion criteria for non-exposed cohort

All subjects must satisfy all of the following criteria at entry into the non-exposed cohort:

- Full date (day/month/year) of first day of LMP available in the database or calculated from EDD (day/month/year)
- Female, aged between, and including, 15 and 25 years of age at LMP
- Recorded in the CPRD **GOLD** since at least 12 months at LMP
- First day of LMP available in the database or calculated from EDD (day/month/year) between September 1st 2008 and June 30th 2011
- At least one dose of *Cervarix* received between September 1st 2008 and June 30th 2011
- Full date (day/month/year) of *Cervarix* vaccination(s) available
- First day of LMP available in the database or calculated from EDD between 120 days and 18 months after the last dose of *Cervarix*
- Subject defined as acceptable in CPRD **GOLD**

(Amended 14 March 2013)

4.2.2.3. Exclusion criterion for exposed cohort

The following criterion should be checked at the time of entry into the exposed cohort. If this exclusion criterion applies, the subject must not be included in this cohort:

- Female with the first day of LMP between 30 days before and 90 days after at least one dose of unspecified HPV vaccine and/or *Gardasil*.

¹ Defined in Appendix A. CPRD **GOLD** indicates whether the patient has met certain quality standards (based on an 'internal CPRD **GOLD** check') **(Amended 14 March 2013)**

4.2.2.4. Exclusion criteria for non-exposed cohort

The following criteria should be checked at the time of entry into the non-exposed cohort. If those exclusion criteria apply, the subject must not be included in this cohort:

- Female with the first day of LMP between 30 days before and 90 days after at least one dose of unspecified HPV vaccine and/or *Gardasil*.
- Female included for a previous pregnancy in the exposed cohort.

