In the US, the commercial distribution of *Cervarix* began in October 2009. However, the uptake of *Cervarix* in the US is lower than expected (234,710 doses were shipped in 2010; 153,730 doses in 2011; **134,720 doses in 2012; and between 100,000 and 150,000 doses are projected for 2013**). Hence, the EPI-HPV-020 study will be unable to reach the target sample size during the scheduled recruitment period (Projected completion of the study: Q2 2015). To address the regulatory requirement from the US FDA, GSK evaluated potential alternatives to the US study and identified a suitable alternative, namely the UK, a country with high vaccine coverage for *Cervarix*, so that these data can be acquired, analyzed and reported to FDA in a timely matter. In the UK, *Cervarix* has been available since September 2008. It is recommended for women between 9 and 25 years of age [*Cervarix*, UK Package Insert, 2011a]. Because *Cervarix* was used exclusively in the public HPV immunization program in the UK from mid-2008 to 2011, this is currently the only country in Europe with sufficient vaccination coverage to undertake an alternative study to the US study.

In the UK, a public immunization programme targeting girls between 12-13 years of age including a catch-up programme for young women up to 18 years was undertaken during the school year 2008/09. A phased catch-up programme for females born 1 September 1991 to 31 August 1995 during the 2008/09 academic year was completed by the end of the 2009/10 academic year. The programme was delivered largely through secondary schools [Crawford, 2009; Sheridan, 2009; Sheridan, 2010].

The present cohort study is an analysis of data collected in the Clinical Practice Research Datalink **General Practitioner OnLine Database (CPRD GOLD)** in the UK. The CPRD **GOLD** is the world's largest computerised database of linked anonymised longitudinal medical records from primary care [Williams, 2012].

(Amended 14 March 2013)

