4. STUDY POPULATION

4.1. Study cohorts

Two cohorts of pregnant women will be defined based on exposure to *Cervarix* as recorded in the CPRD **GOLD** (Figure 1) **(Amended 14 March 2013)**:

- The **exposed cohort** will include women with the first day of LMP: between 30 days before and 45 days after any *Cervarix* dose, as requested by the FDA, and between 30 days before and 90 days after any *Cervarix* dose, as defined in the study EPI-HPV-020 and as used for the pooled analysis by Wacholder [Wacholder, 2010].
- The **non-exposed cohort** will include women with the first day of LMP between 120 days and 18 months after their last *Cervarix* dose (and no further *Cervarix* dose before the outcome).

Figure 1 Definition of exposure and non-exposure

Note: Last dose can be first or second dose if no subsequent dose was administered.

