4.2.2.1. Inclusion criteria for exposed cohort

All subjects must satisfy all of the following criteria at entry into the exposed cohort:

- Full date (day/month/year) of first day of LMP available in the database or calculated from Estimated date of delivery (EDD) (day/month/year)
- Female, aged between, and including, 15 and 25 years of age at LMP
- Recorded in the CPRD *GOLD* for at least 12 months at LMP

- First day of LMP available in the database or calculated from EDD (day/month/year) between September 1st 2008 and June 30th 2011
- At least one dose of *Cervarix* received between September 1st, 2008 and June 30th, 2011
- Full date (day/month/year) of *Cervarix* vaccination(s) available
- First day of LMP available in the database or calculated from EDD between 30 days before and 90 days after any dose of *Cervarix*
- Subject defined as acceptable in CPRD **GOLD**¹

(Amended 14 March 2013)

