5.5.1. Subject disposition

Subject disposition will be summarized by computing:

- Number of screened subjects.
- Number (%) of non-eligible subjects for each of the following reasons of non-eligibility:
 - No certainty of *Cervarix* vaccination
 - All *Cervarix* doses outside September 1th 2008 and June 30th 2011
 - No pregnancy identifiers
 - First day of LMP outside September 1th 2008 and June 30th 2011
 - Age at first day of LMP outside 15 – 25 years
 - Start in CPRD **GOLD** less than one year before first day of LMP
 - Subject not flagged as acceptable in CPRD **GOLD**
 - Neither in the exposed nor non-exposed cohort.
- Number of eligible subjects in each cohort.
- Number of included subjects in each cohort.

A detailed, comprehensive list of reasons for elimination from exposed and non-exposed cohort analyses will be established at the time of data cleaning.

(Amended 14 March 2013)

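### The comparator's washout before LMP is 120 days for Cervarix-coded doses but only 90 days for unspecified HPV vaccine or Gardasil, leaving an unexplained 29-day gap

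*Combined protocol and SAP*

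**What the plan says.** Section 4.2.2.2 admits a woman to the non-exposed cohort if her LMP lies "between 120 days and 18 months after the last dose of" Cervarix. Section 4.1 adds the condition "and no further *Cervarix* dose before the outcome". Both rules name Cervarix only.

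Other HPV doses are handled by a separate exclusion in section 4.2.2.4: a "Female with the first day of LMP between 30 days before and 90 days after at least one dose of unspecified HPV vaccine", or of Gardasil. Section 4.2.2.3 applies the same exclusion to the exposed cohort.

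On which product was in use, section 1.2 states that Cervarix "was used exclusively in the public HPV immunization program in the UK from mid-2008 to 2011". Section 5.5.1 nevertheless lists "No certainty of *Cervarix* vaccination" among the reasons for non-eligibility, so the plan expects some doses whose brand is not established. The HPV codes given in sections 3.2 and 4.2.1 identify the dose number, not the brand. Cohort algorithms are left to Appendix A, whose full text is not in the material reviewed.

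**The concern.** The design leaves a buffer: an LMP 91 to 119 days after a Cervarix dose belongs to neither cohort. Section 3.2 rests the comparator on the delay between vaccination and gestation, and the buffer protects that delay. It does not apply to a dose whose brand was not recorded. Two women with identical vaccination dates can thus be classified differently only because of how one dose was coded.

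If the unspecified dose was in fact Cervarix, the comparator contains women vaccinated more recently than the design intends. Any raised risk that persisted past 90 days would then be present in both arms, pulling the hazard ratio toward 1. Section 5.3 states an alternative of increased risk, so this is the unfavourable direction for a safety study.

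**Working it through.** **Rules side by side, for the non-exposed cohort**

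| Dose before LMP | Coded Cervarix | Unspecified or Gardasil, with an earlier Cervarix-coded dose 120 days to 18 months before LMP |
|---|---|---|
| 0 to 90 days | not a comparator | excluded by 4.2.2.4 |
| 91 to 119 days | in neither cohort | **kept as comparator** |
| 120 days or more | comparator | comparator |

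The gap is 119 − 91 + 1 = 29 days. For example, a woman with a Cervarix-coded dose 200 days before LMP and an unspecified dose 100 days before LMP is a comparator. With the second dose coded Cervarix she drops out. Nothing in the available text closes or explains the difference. Section 1.2 describes the US study's comparator as starting 120 days after the last Cervarix or Gardasil dose, so that design runs the longer clock for both brands.

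**The plan's power figures.** Inputs: 243 or 379 exposed and 667 non-exposed (section 3.2); 11.5% risk, 20% dropout, two-sided 5%, HR 2.0 (section 5.4). Freedman form, with k = n1/n0 and E the expected events:

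z = √(E·k) × (HR − 1)/(1 + k·HR) − 1.96

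With dropout spread exponentially over follow-up, λ = −ln(0.885) = 0.1222 and γ = −ln(0.8) = 0.2231. The event probability at hazard h is h/(h + γ) × (1 − e^−(h+γ)): 0.1033 for h = λ and 0.1952 for h = 2λ.

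- −30/+45 window: E = 243 × 0.1952 + 667 × 0.1033 = 116.3 and k = 0.364, so z = 6.51 × 0.5785 − 1.96 = 1.81 and power is 96.5% (plan: 98%).
- −30/+90 window: E = 142.9 and k = 0.568, so power is 98.8% (plan: 99%).
- HR detectable at 80% power: 1.72 and 1.63 (plan: 1.69 and 1.60).

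Power reproduces to within 2 points; 96.5% is the baseline below.

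**Size of the gap.** The documents give no count of unspecified doses, so this is a range under assumptions. Taking 18 months as 548 days, the comparator window spans 548 − 120 + 1 = 429 days.

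- At the comparator's LMP density: 667/429 × 29 = 45 women in a 29-day band.
- At the density of days 46 to 90: (379 − 243)/45 × 29 = 88 women.

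Let u be the assumed share of doses at that distance that are unspecified. The affected fraction is c = u × band/667. If the full HR of 2.0 still acts at 91 to 119 days (worst case), the observed HR is 2/(1 + c).

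| u (assumed) | Women affected | c | Observed HR | Power | Power if removed |
|---|---|---|---|---|---|
| 5% | 2 to 4 | 0.3% to 0.7% | 1.99 | 96.3% to 96.2% | 96.4% |
| 20% | 9 to 18 | 1.4% to 2.6% | 1.97 to 1.95 | 95.9% to 95.3% | 96.4% to 96.3% |
| 50% | 23 to 44 | 3.4% to 6.6% | 1.94 to 1.88 | 95.0% to 93.2% | 96.2% to 96.0% |

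These counts lean high, because each affected woman must also have an earlier Cervarix-coded dose, so an unspecified first dose cannot place her in the gap.

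**The same exclusion in the exposed cohort.** Section 4.2.2.3 removes a woman with a dated Cervarix dose in the window if an unspecified dose also falls within −30/+90 days. If 5% or 10% of the 243 were lost this way (assumed), power would be 96.0% or 95.5%.

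**The case against.** The exclusion in 4.2.2.4 covers the whole −30/+90 period, and so both risk windows the plan defines. Days 91 to 119 lie outside them, and dilution needs an effect lasting beyond 90 days, which the plan does not posit. This largely stands and is why the point is small. One qualification concerns dating. Table 6 (section 5.2.5.2) leaves LMP discrepancies of up to 7, 14 or 21 days uncorrected, so a woman dated 91 to 111 days after a dose could truly lie within 90 days. That reaches only the secondary window, since 91 − 21 = 70 is still beyond 45.

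A second objection is that Appendix A must hold a rule for telling Cervarix from unspecified doses, and that rule may resolve most unbranded records. This also stands: the gap could be nearly empty.

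Three stronger readings are tempting, and the documents do not support them:

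- *That the plan itself makes the unspecified dose almost certainly Cervarix.* Section 1.2 speaks only of the public programme, and sections 4.2.2.3 and 4.2.2.4 group unspecified vaccine with Gardasil.
- *That 83,686 − 78,111 = 5,575 (6.7%) measures the problem.* Those are women aged 15 to 25 not counted as Cervarix-exposed. An affected woman must have a Cervarix-coded dose and also an unspecified one, and the two counts may cover different periods.
- *That the exposed-cohort exclusion discards women for no gain and should be relaxed in the primary analysis.* Model 3 (section 5.6.3.1) classifies exposed women by number of Cervarix doses, which an unspecified dose makes indeterminate. The exclusion also keeps out possible mixed-product exposure. It is a defensible trade-off.

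**Conclusion.** The mismatch is explicit and unexplained: 120 days for Cervarix-coded doses, but 91 days or more suffices for unspecified HPV vaccine or Gardasil. It lets into the comparator women whom the design would place in neither cohort if the brand had been recorded as Cervarix.

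The number affected cannot be fixed from the documents. Under the assumed shares, a true HR of 2.0 would be seen as 1.99 to 1.88; the lower end needs half of the doses at that distance to be unspecified and the full effect to persist past 90 days. The likely effect is small and toward the null. It does not threaten the study's conclusions, but none of the planned sensitivity models tests it. A correction is justified because it is cheap and removes an avoidable bias in the unfavourable direction.

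**What to change.** 1. In section 4.2.2.4, require that no HPV vaccine dose of any brand, or of unspecified brand, falls within the 119 days before LMP, matching the 120-day Cervarix rule. Keep the existing bar on such doses in the 30 days after LMP.
2. Add one Model 1 sensitivity analysis that counts unspecified HPV doses given from September 2008 to June 2011 as Cervarix in both cohorts. In that run the exclusions apply to Gardasil only, which restores women with a Cervarix-coded dose in the window whom section 4.2.2.3 removes only because of an unspecified companion dose.
3. Leave the exposed-cohort exclusion in the primary analysis as it is.

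The cost is one edited criterion, one extra model run on the same extract, and a few comparator pregnancies. In the calculations above, removing those women leaves power at 96.0% or higher against a baseline of 96.5%.

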4.3. Included population

It is planned to include all eligible pregnant women in each of the two cohorts.

All included subjects will be followed until: end of pregnancy, subject de-enrolment from CPRD *GOLD* or study termination.

(Amended 14 March 2013)

5. DATA EVALUATION: CRITERIA FOR EVALUATION OF OBJECTIVES

5.1. Endpoints

5.1.1. Primary endpoint

- Occurrence of spontaneous abortion² during weeks 1-23 of gestation

5.1.2. Secondary endpoints

- Occurrence of spontaneous abortion during weeks 1-19 of gestation
- Occurrence of other pregnancy outcomes:
 - Induced/therapeutic and other abortions (according to UK and US definitions of spontaneous abortion)
 - Stillbirth (according to UK and US definitions of stillbirth)
 - Birth defects identified among all pregnancies with known outcome classified as live births, stillbirths and abortions. For live births, birth defects identified within the first 12 weeks of life will be included
 - Small/Large for gestational age at birth
 - Pre-term and post-term delivery
- Baby's death in the first 12 weeks of life.

² Refer to GLOSSARY OF TERMS for definition of spontaneous abortion and of the other pregnancy outcomes

5.2. Data collection

5.2.1. The Clinical Practice Research Datalink *General Practitioner OnLine Database (CPRD GOLD)*

The CPRD *GOLD* is the world's largest computerised database of linked anonymised longitudinal medical records from primary care. The data are drawn from the computer systems used by general practitioners to maintain the clinical records within their practices. As of March 2011, CPRD *GOLD* contained records from over 12 million patients contributing 64 million person-years of prospectively recorded high-quality primary healthcare data [Williams, 2012].

The CPRD *GOLD* is operated on a non-profit basis by the MHRA, containing coded longitudinal medical records from general practices and more recently from hospital-based care (e.g., Hospital Episode Statistics, HES). The current linkage between CPRD *GOLD* primary care data and HES data is around 40% as of Q1 2012. The CPRD *GOLD* database is licensed in-house by GSK. Data quality is monitored continuously by the MHRA and practices that fail to maintain the required standards are removed from the database.

The latest update provided by the CPRD *GOLD* team in Q3 of 2012 (second release of 2012) contains data for 10,547,532 research standard patients, drawn from 644 practices throughout the UK. A total of 4,621,799 patients from **546** practices are currently active in the database. The CPRD *GOLD* population closely matches the age and gender distribution of the UK population as a whole. Mean follow-up is 6.8 years (median 5.0 years). Recorded data include demographic information, prescription details, clinical events, preventive care provided, specialist referrals, hospital admissions and their major outcomes. Data are retrieved by means of the READ classification system; READ codes are a coded thesaurus of clinical terms, which are the basic means by which clinicians record patient findings and procedures in health and social care IT systems across primary and secondary care (e.g. *general practitioner [GP]* surgeries and pathology reporting of results). The Medcodes are the abbreviated terms which mean CPRD *GOLD* medical codes. Medcodes consisting of READ codes are used to enter medical diagnosis in the CPRD *GOLD* database.

The use of the CPRD *GOLD* database for research on pregnancies has been reported in a few publications. Devine *et al* have developed an algorithm for identification of pregnancies [Devine, 2010]. Hardy *et al* have used CPRD *GOLD* records, for linking mother and baby automated records and to describe the frequency, type and pregnancy risk level of medications prescribed prior to and during early pregnancy [Hardy, 2006]. The CPRD *GOLD* database has been also assessed as an alternative for pregnancy registries to study drug exposure [Charlton, 2008], major congenital malformations [Charlton, 2010], and identification of potential teratogens [Charlton, 2011].

Data will be automatically extracted from the second release of 2012 (2012Q3) available in GSK, using the algorithms defined in the Appendix A. In addition, specific free text associated with endpoints (e.g. pregnancy outcomes), will be requested where necessary for endpoint confirmation. The free text request will be sent by GSK to CPRD *GOLD*.

Extracted free text will be de-identified before sending to GSK. Review of free text will be done by a GSK identified reviewer (Pallas, Health research and consultancy B.V) for completing extracted data; a final case ascertainment step will be performed as described in section 5.2.4.2, 5.2.4.3 and 5.2.6.

The final study database will consist of data extracted from CPRD **GOLD** and additional data from free text review. The study database will be locked and stored by GSK Biologicals' data management.

(Amended 14 March 2013)

5.2.2. Validation of the CPRD **GOLD database**

The CPRD **GOLD** database is licensed in-house by GSK. GSK has not audited CPRD **GOLD**, but CPRD **GOLD** has internal procedures to ensure the quality of data. The use of the CPRD **GOLD** database is well documented and it has been used by both MHRA and FDA.

(Amended 14 March 2013)

5.2.3. Study period

Study period will include women being vaccinated with *Cervarix* and with the first day of LMP between September 1st 2008 and June 30th 2011 and followed for pregnancy outcomes until June 25th 2012 (considering 9 months of pregnancy and 12 weeks after delivery). The 2012Q3 database is up to June 25th 2012.

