5.2.4.2. Pregnancy outcomes

Pregnancy outcomes will be identified using defined algorithms (see Appendix A).

Definition of pregnancy outcomes (according to the UK or US definition):

1. Abortion defined as a loss of pregnancy with the first 23 weeks (≤ 161 days) or within the first 19 weeks (≤ 133 days) of gestation, with the following sub-categories:
 1. Spontaneous abortion
 2. Induced / therapeutic abortion
 3. Other abortion
2. Stillbirth defined as intra-uterine death of foetus after 23 weeks (>161 days) or after 19 weeks (> 133 days) of gestation
3. Live births, with the following sub-categories:
 1. Small for gestational age at birth
 2. Large for gestational age at birth
 3. Pre-term delivery (< 37 weeks of gestation)
 4. Full term delivery (between 37 weeks and 42 completed weeks of gestation)
 5. Post-term delivery (> 42 *completed* weeks of gestation)

(Amended 14 March 2013)

Confirmation of pregnancy outcomes (according to the UK or US definition):

For each pregnancy, the gestational age at outcome will be computed in days as:

- $\text{Gestational_age (days)} = (\text{date of outcome}) - (\text{date of first day of gestation}) + 1$

All abortions and stillbirths will be confirmed using this gestational age:

- if $\text{gestational_age} \leq 161$ days or ≤ 133 days, \rightarrow abortion is confirmed

- if gestational_age > 161 days or > 133 days, → stillbirth is confirmed

For all the identified cases of spontaneous abortion, other abortion, and stillbirth, the associated free text will be reviewed by a GSK-identified reviewer for sub-category classification (spontaneous, induced/therapeutic, and others). As far as possible, other abortion will be re-classified as spontaneous or induced/therapeutic abortion.

Cases of live birth will be classified as pre-term, full term and post-term delivery based on the gestational age at delivery:

- if gestational_age < 259 days then pre-term delivery is confirmed
- if gestational_age \geq 259 and \leq 294 days then full term delivery is confirmed
- if gestational_age > 294 days then post-term delivery is confirmed

Cases of live birth for which confirmation of pre-term, full term or post-term delivery is not possible because the gestational age is missing will be classified as non-confirmed pre-term, full term or post-term delivery, respectively.

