5.2.4.3. Baby (live birth) characteristics and confirmation of birth defects

The baby will be identified using the Mother-Baby link (MBL) available in CPRD **GOLD**. In case of multiple pregnancy, all babies will be followed.

For the live births, the following baby characteristics at birth will be extracted:

- Gender
- Weight
- Length

- Apgar score (at 1 minute and 5 minutes of life)

Codes related to baby's death within 12 weeks of life will be extracted with the associated free text.

Birth defects reported in the mother's file and/or in the baby's files within 12 weeks after delivery will also be extracted with the associated free text.

All cases with an identified birth defect will be reviewed by a GSK Safety physician using the birth defects classification by the CDC Metropolitan Atlanta Congenital Defect Program or MACDP [Centers for Disease Control and Prevention, 2004 and Centers for Disease Control and Prevention, 2007]. Cases with apparent birth defects will be described in detail. Link between medical codes in CPRD *GOLD* and MACDP terminology is detailed in Appendix A.

(Amended 14 March 2013)

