5.2.5. Derived variables

5.2.5.1. First day of LMP

Definition of first day of LMP will be as follows:

1. The date of first day of LMP as reported in the database
2. If date of first day of LMP is missing or LMP date is equal to system date (± 2 days) but the EDD is completed in CPRD *GOLD*, the first day of LMP will be calculated as follows: EDD-280 days (*280 days equal to the median of gestational age: 40 weeks*).

(Amended 14 March 2013)

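### The denominators for baby's death and birth defects do not require a live birth, a Mother-Baby link or 12 weeks of baby record, so unobserved babies count as non-cases

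*Combined protocol and SAP*

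**What the plan says.** Section 5.1.2 lists baby's death in the first 12 weeks of life as a secondary endpoint. It gives birth defects the same window: "For live births, birth defects identified within the first 12 weeks of life will be included".

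Section 5.2.3 admits women with "first day of LMP between September 1st 2008 and June 30th 2011", "followed for pregnancy outcomes until June 25th 2012 (considering 9 months of pregnancy and 12 weeks after delivery". It adds: "The 2012Q3 database is up to June 25th 2012".

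Section 5.2.4.3 states: "The baby will be identified using the Mother-Baby link (MBL) available in CPRD" GOLD. Birth defects are taken from the mother's file, the baby's file or both. For deaths, the section says that codes and free text will be extracted but not from which file.

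Four sections bear on the analysis:

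- Section 5.5.3.2 divides the cases of each outcome by the women whose pregnancy outcome is known.
- Section 5.6.2 divides the cases by all pregnancies.
- Section 5.6.3.2 models baby's death and birth defect as binary outcomes, with no stated restriction on who enters the model.
- Section 5.5.2 reports the proportion of mother-baby links as a descriptive item only.

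Section 5.6.1 says that missing data will not be filled in. Section 4.3 says: "All included subjects will be followed until: end of pregnancy, subject de-enrolment from CPRD" GOLD, or study termination. It does not mention the 12 weeks after birth.

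**The concern.** The two denominators differ, and neither is the set of babies in whom the event could have been seen. A live birth with no link still has a known pregnancy outcome. It stays in the denominator, and if no event code is found for it, it enters the analysis as a non-case. The same holds for a linked baby whose record stops before 84 days.

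The plan deals with incomplete information elsewhere. Section 5.2.4.2 creates non-confirmed categories when gestational age, or both birth weight and length, are missing. It has no counterpart for death or birth defects.

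At stake are two secondary safety endpoints. Their proportions would be understated, and the exposed-to-non-exposed odds ratio would be biased if linkage or length of record differs between cohorts. Section 5.6.3.2 also drops the logistic model when an outcome has fewer than 10 cases, so unseen events can remove a comparison altogether.

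**Working it through.** **1. The plan's own date statement.** Last LMP June 30th 2011 (5.2.3) plus nine calendar months is March 30th 2012. Adding 84 days gives June 22nd 2012, three days inside the June 25th 2012 cut-off. On its stated basis, section 5.2.3 holds.

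**2. The same check on the plan's pregnancy lengths.** From June 30th 2011 to June 25th 2012 is 361 days. Twelve full weeks are therefore available for the last LMP only if delivery comes within 361 − 84 = 277 days.

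- Section 5.2.5.1 uses "280 days equal to the median of gestational age: 40 weeks". June 30th 2011 + 280 = April 5th 2012. Days observed: 361 − 280 = 81 of 84, a shortfall of 3.
- Section 5.2.4.2 sets the upper limit of full term: "if gestational_age > 294 days then post-term delivery is confirmed". It counts gestational age as date difference plus 1, so 294 days means LMP + 293, or April 18th 2012. Days observed: 361 − 293 = 68 of 84, a shortfall of 16.
- The LMP window from September 1st 2008 to June 30th 2011 has 1,033 days. Share of LMP dates affected: 3/1,033 = 0.3% at 280 days and 16/1,033 = 1.5% at gestational age 294. Post-term births fall somewhat further short.

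The cut-off is thus a minor contributor.

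**3. Who is counted and who is observed.** Take a live birth with no Mother-Baby link:

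- under 5.5.3.2 the outcome is known, so it is in the denominator;
- under 5.6.2 it is a pregnancy, so it is in the denominator;
- under 5.2.4.3 no baby file is reached, so a defect recorded only there cannot be seen, and a death can be seen only if the mother's file is searched;
- under 5.6.1 nothing is flagged as missing, because an event code that was never written looks the same as an event that did not happen.

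As written, the result is a non-case.

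**4. Effect on the proportion.** For an event visible only in the baby's file, observed proportion = true proportion × share of live births observed. The documents give no linkage rate. With an assumed unlinked share of 10–30%, the factor is 0.90 to 0.70, so the proportion is understated by 10–30%. At 30% unlinked, reaching 10 observed cases takes 10/0.70 = 14.3 true ones.

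**5. Effect on the odds ratio.** Assume a true risk of 2% in both cohorts, so the true OR is 1.

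- Equal shares, for example 80% and 80%: 1.6% against 1.6%, OR 1.0.
- 80% against 70%: (0.016/0.984)/(0.014/0.986) = 1.145; reversed, 0.873.
- 90% against 70%: (0.018/0.982)/(0.014/0.986) = 1.29; reversed, 0.77.

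These shares are illustrations. Nothing in the documents shows that linkage differs by cohort.

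**The case against.** Several stronger readings are tempting, and the documents do not support them.

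- *The cut-off date is wrong.* It is not, on the nine calendar months that section 5.2.3 names. The 280 days come from a rule for deriving LMP from the expected delivery date, and even there the shortfall is 3 days.
- *Unlinked babies are not observed at all.* Section 5.2.4.3 also takes birth defects from the mother's file. The gap concerns deaths, if only the baby's file is searched, and defects recorded only in that file.
- *Deaths are sought only in the baby's file.* The plan does not name the file. It also does not say whether a baby who dies early has a record, so no argument can rest on that.
- *The plan declares unobserved babies event-free.* No sentence says so; it follows from the denominators. One could read section 5.6.1 as leaving such babies out, and the bodies of Appendices A and B, which hold the algorithms and table templates, are not in the text available. A rule there cannot be excluded. Section 5.6.1 alone does not settle it, for the reason in step 3 of the working.
- *Calendar truncation biases the cohort comparison.* The direction is plausible. A woman with an LMP at the end of June 2011 is non-exposed if her last dose was up to 120 days before, in early March 2011, while exposure in the −30 to +45 day window needs a dose from mid-May 2011. Table 2 shows 29,364 vaccinations in 2010 and 2,586 in 2011. But about 1.5% of LMP dates at term leaves little room for an effect.
- *Section 4.3 cancels the 12-week follow-up.* It can be read as covering the women only, and section 5.2.4.3 says that all babies of a multiple pregnancy are followed. This is a wording conflict to reconcile.

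It is also fair to say that equal linkage leaves the OR near 1, and that baby's death may not reach 10 cases in any event: with 243 + 667 = 910 women, 10 cases is 1.1%. What remains is that the main text gives two denominators and ties neither to observation.

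**Conclusion.** The concern holds for the denominators. As written, sections 5.5.3.2, 5.6.2 and 5.6.3.2 keep live births without a link, or with less than 84 days of record, as non-cases for baby's death and for defects found only in the baby's file. The understatement is roughly the unobserved share, about 10–30% under the assumed range, and it could be smaller or larger because no rate is given. Bias in the OR depends on unequal observation between cohorts, which is possible but not shown.

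The conclusion assumes that the appendices contain no rule restricting these analyses. It concerns secondary endpoints only; the primary analysis of spontaneous abortion to week 23 does not depend on it.

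**What to change.** - In 5.5.3.2, 5.6.2 and 5.6.3.2, set one denominator for baby's death: live births with a Mother-Baby link that are observed to 84 days of life or to death.
- For birth defects, apply the same restriction to the live-birth part, and keep stillbirths and abortions as planned.
- State in 5.2.4.3 that death codes are searched in both the mother's and the baby's files.
- Add a sensitivity analysis over all live births that includes events found only in the mother's file. Without it, the restriction would discard deaths in unlinked babies, and it would mislead if linkage is related to the baby's outcome.
- In 5.5.2, report per cohort the numbers of live births, of those linked, and of those observed to 12 weeks.
- Reconcile 4.3 with the 12-week endpoints.

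No separate LMP limit is needed: the observation rule already handles the cut-off, and an earlier last LMP would drop babies who are fully observed.

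The cost is protocol wording, one eligibility flag and one code search in data already held. The downside is somewhat fewer live births in these secondary endpoints.
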